#### 9.4.3 ANALYSIS OF THE SECONDARY ENDPOINT(S)

Analysis of secondary endpoints will be independent of analysis of primary endpoints. All secondary endpoints will be measured as continuous variables and will be reported as adjusted means with standard deviations. Repeated measures one-way ANOVA and paired Student's *t*-tests will be used for analyses. If there are significant interactions differences between pairs of means will be determined with a Bonferroni *post-hoc* test. Missing data will be imputed using mean imputation from all other measurements collected from the given participant. Outliers will be included and excluded in independent analysis, both of which will be reported.

---

#### 9.4.4 SAFETY ANALYSES

Safety analysis will be performed using summary statistics during treatment interventions. Adverse events will be coded according to the Medical Dictionary for Regulatory Activities and will have severity, and relationship of adverse event to study intervention presented by System Organ Class and preferred term groupings. Each instance of an adverse event will be presented as a discrete event. Duration of events, severity, relationship to intervention, expectation, and outcome will be presented. Adverse events that lead to premature discontinuation will be presented in a table, along with all treatment-emergent serious adverse events.

---

#### 9.4.5 BASELINE DESCRIPTIVE STATISTICS

Baseline characteristics of participants will be presented in a table. No descriptive statistics other than mean and standard deviation will be presented as the proposed study uses a within-subjects design.

---

#### 9.4.6 PLANNED INTERIM ANALYSES

No interim analysis is planned for the proposed study. *Phase I* of this study will be completed in advance of *phase II*, and as such efficacy and safety analyses for *phase I* may occur before the completion of *phase II*. The results of *phase I* will not be used to modify the desired sample size or planned analyses of *phase II*.

---

#### 9.4.7 SUB-GROUP ANALYSES

Sub-analysis of each primary and secondary endpoint will be performed based upon sex. This analysis will be performed identically to all efficacy and safety analyses with the only adjustment being the exclusion of the sex not of interest.

---

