Continuous blood pressure, heart rate, and electrocardiogram monitoring will occur prior to, and during cannabis administration (prior to exercise) on all visits where cannabis is consumed. This procedure will be followed throughout the entirety of the 40-minute cannabis consumption period. If either systolic or diastolic blood pressure exceeds 160mmHg or 90mmHg at rest, respectively, exercise will not be performed, and the study visit will not continue. If heart rate exceeds 100bpm or falls below 40bpm at rest, exercise will not be performed, and the study visit will not continue.

All research will be performed within the department of Human Health and Nutritional Sciences at the University of Guelph.

There are no planned interim analyses planned for the current trial.

A sub-group analysis will be performed, with participants divided by sex, to determine the existence of any sex differences in primary and secondary endpoints.

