## 9 STATISTICAL CONSIDERATIONS

### 9.1 STATISTICAL HYPOTHESES

- Primary Efficacy Endpoint(s):
  1. Pulse Wave Velocity will be increased following exercise, smoking high THC cannabis, and vaporizing high THC cannabis relative to resting baseline; effects of cannabis consumption and exercise are likely to be additive. Vaporizing high CBD cannabis will not increase pulse wave velocity.
  2. Percent flow mediated dilation will be decreased following exercise and smoking high THC cannabis; effects are likely to be additive. Vaporizing both high THC and high CBD cannabis will not decrease percent flow mediated dilation.
  3. Ejection fraction will be decreased following smoking and vaporizing high THC cannabis. Exercise and vaporization of high CBD cannabis will not be associated with reductions in ejection fraction.
  4. E/A Ratio will be decreased following high THC cannabis smoking only.
  5. Myocardial strain will be decreased following high THC cannabis smoking and vaporizing only.
  6. Myocardial twist will be decreased following high THC cannabis smoking and vaporizing only.
  7. Burst Frequency will be increased following high THC cannabis only.
  8. Burst Incidence will be increased following high THC cannabis only.

- Secondary Efficacy Endpoint(s):
  1. Systolic Blood Pressure will be increased following cannabis consumption and will be decreased following all bouts of exercise.
  2. Diastolic blood pressure will be unchanged under all conditions
  3. Heart rate will be increased following cannabis consumption and exercise.
  4. Stroke volume will be increased with exercise, and will be reduced following cannabis consumptions. These competing effects will result in an attenuation of increases in stroke volume when exercise is preceded by cannabis consumption.
  5. Cardiac output will be unchanged under all conditions
  6. Work completed will be reduced when preceded by cannabis consumption of all forms
  7. Average power output will be reduced when preceded by cannabis consumption of all forms
  8. Oxygen consumption will be reduced when exercise is preceded by consumption of high THC cannabis
  9. Rating of Perceived Exertion will be increased following consumption of high THC cannabis
  10. Rate-pressure product will be increased during exercise, when the bout is preceded by cannabis consumption.

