## 9.4 STATISTICAL ANALYSES

### 9.4.1 GENERAL APPROACH

Our study will be divided into two phases each of which will be analyzed independently. All tests of significance will be two-tailed, and statistical significance will be based upon an alpha error probability of 5% and a power for 80%. The data will be evaluated using both parametric and non-parametric tests, as applicable. If the data are found to be not normally distributed, the raw data will be transformed using an appropriate transformation model in order to perform the parametric assessments. Non-parametric tests will be performed on raw data. The data will be assessed as continuous and will be presented as means with standard deviations. A one-way analysis of covariance will be used to assess the treatment

effects (Phase I: exercise, vaporizing THC, smoking THC, vaporizing + exercise THC, smoking THC + Exercise, Phase II: exercise, vaporizing THC, vaporizing CBD, vaporizing + exercise THC, Vaporizing CBD + Exercise) on the primary endpoints. Covariates will be introduced into the models in order to assess the impact of certain potential factors on outcome, including fitness, blood pressure, resting heart rate, and any other factors that are observed during the study that appear to potentially influence the outcome.

Our secondary endpoints will be assessed using a repeated measures one-way ANOVA and paired t-tests. If there are significant interactions differences between pairs of means will be determined with a Bonferroni post-hoc test.

---

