#### 9.4.9 EXPLORATORY ANALYSES

There are no planned exploratory analyses in the current study.

---

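### Every primary and secondary endpoint is re-tested at 5% within each sex (36 tests in Phase I, 32 in Phase II) with no error control and no exploratory label

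*Protocol*

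**What the plan says.** Protocol 9.4.7, repeated in item 7 of section 4 of the SAP, sets the scope: "Sub-analysis of each primary and secondary endpoint will be performed based upon sex". It sets the method as "performed identically to all efficacy and safety analyses with the only adjustment being the exclusion of the sex not of interest".

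The threshold is therefore the one in Protocol 9.4.1: "All tests of significance will be two-tailed", with alpha 5%. Protocol 4.1 gives the purpose of the sex split: "to determine the existence of any sex differences in primary and secondary endpoints". Protocol 9.4.9 and its SAP counterpart add: "There are no planned exploratory analyses in the current study". The tertiary/exploratory row of the objectives table in section 3 is marked not applicable.

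Protocol 9.1 lists 8 primary hypotheses, the last being "Burst Incidence will be increased following high THC cannabis only", and 10 secondary ones. The only multiplicity device (9.4.1, 9.4.3) is a Bonferroni post-hoc comparison between pairs of means for secondary endpoints. Section 5.5 plans 10 women and 10 men per phase. Section 9.2 bases its power statement on 15 participants.

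**The concern.** Repeating every analysis in each half of the sample doubles the number of 5% tests. The plan does not say that the repeats are weaker evidence than the main analysis. Its only statement on exploratory status is that no such analyses exist, and 4.1 gives the sex split an inferential aim.

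The risk is a reported effect in women only, or in men only, that is chance and rests on 7 to 10 people. Low power adds to this. A real effect of the same size in both sexes can easily reach significance in one and miss it in the other, which would then look like a sex difference.

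**Working it through.** **The plan's own figure.** Section 9.2 requires 15 participants for power of at least 0.80 at alpha 0.05. It does not give the pre-post correlation r. For a two-sided paired t-test, SD of the difference = √(s₁² + s₂² − 2r·s₁·s₂). At an assumed r = 0.5:

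- Strain: √(1.44 + 3.61 − 2.28) = 1.664; 1.3/1.664 = 0.781; n = 15 (power 0.803).
- FMD after exercise: √(6.25 + 2.89 − 4.25) = 2.211; 2.1/2.211 = 0.950; n = 11.
- PWV: √(1.69 + 1.69 − 1.69) = 1.300; 1.4/1.300 = 1.077; n = 9.

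So 15 is reproduced by strain at r = 0.5. At r = 0 the three need 26, 19 and 16; at r = 0.7 they need 11, 8 and 7.

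**Number of within-sex tests**, at one test per hypothesis in 9.1:

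- Phase I: (8 + 10) × 2 = 36.
- Phase II: (8 − 2 + 10) × 2 = 32. The two burst endpoints drop out because section 4.1 limits microneurography to a single visit and the schedule (1.3) places it at Visit 2, in Phase I.

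**Expected false positives**, with no true effects and each test at 5%: 36 × 0.05 = 1.8 and 32 × 0.05 = 1.6. These do not depend on correlation.

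**Chance of at least one.** With k endpoints per sex and the sexes independent, it is 1 − (1 − F)², where F is the chance of at least one false positive among k tests in one sex. With independent endpoints F = 1 − 0.95^k, giving 1 − 0.95³⁶ = 84% and 1 − 0.95³² = 81%. The documents give no correlation between endpoints, so it is varied, taken as equal for all pairs:

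| Correlation | F, k = 18 | Phase I | F, k = 16 | Phase II |
|---|---|---|---|---|
| 0 | 0.603 | 84% | 0.560 | 81% |
| 0.5 | 0.398 | 64% | 0.374 | 61% |
| 0.6 | 0.338 | 56% | 0.319 | 54% |
| 0.7 | 0.277 | 48% | 0.264 | 46% |
| 0.8 | 0.216 | 39% | 0.207 | 37% |

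**If some effects are real.** As an illustration, treat PWV, FMD, heart rate, stroke volume, cardiac output and rate-pressure product as truly affected by exercise. Also drop one of work and average power, which are the same quantity over a fixed 20 minutes. That leaves 18 − 6 − 1 = 11 true nulls per sex in Phase I and 16 − 6 − 1 = 9 in Phase II. Expected false positives are 22 × 0.05 = 1.1 and 18 × 0.05 = 0.9. The chance of at least one is 52% and 47% at correlation 0.5, and 46% and 42% at 0.6.

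**If the one-way ANCOVA is run literally.** A one-way test that ignores the repeated measurements is conservative. Simulating five conditions in 8 to 10 people without covariates gives a type I error of about 1.3 to 1.4% at within-person correlation 0.3, and about 0.4% at 0.5. The primary endpoints would then add little. The 10 secondary endpoints in two sexes still make 20 tests: 1.0 expected false positive, and 1 − 0.95²⁰ = 64% if independent.

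**Power within a sex.** Take the standardised change with 80% power at n = 15, which is 0.778. Power is the probability that a noncentral t (n − 1 degrees of freedom, noncentrality 0.778√n) exceeds the two-sided 5% limit. It is 0.59 at n = 10, 0.48 at n = 8 and 0.41 at n = 7. The last two are an even split of 15 completers. This matches strain at r = 0.5. At the same r, power at n = 10 is 0.76 for FMD and 0.86 for PWV. Over r = 0 to 0.7, power at n = 10 runs from 0.37 to 0.77 (strain), 0.50 to 0.91 (FMD) and 0.58 to 0.97 (PWV).

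**The case against.** A reader might infer that a false sex-specific finding is more likely than not, at about two per phase, whatever the truth. The documents do not support that. It needs every endpoint to be null in both sexes, correlation below about 0.65, and tests that hold 5%. Section 2.1 describes exercise as an established cause of stiffening, endothelial impairment and cardiac load, and section 3 calls several exercise responses well characterised. The primary analysis as written is conservative if taken literally. This part of the objection stands, so the probabilities are conditional.

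A reader might also infer that the plan gives a within-sex result the same standing as the full-sample result, or lets it replace a null one. No text says so. The wording "This analysis will be performed identically to all efficacy and safety analyses" describes method, the main analyses are defined separately in 9.4.2 and 9.4.3, and the sex analyses sit under a sub-group heading. This also stands. What remains is that nothing marks the within-sex tests as weaker, while 9.4.9 denies that any analysis is exploratory.

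Third, the 59% power figure is the weakest of the three pilot endpoints. That is correct, and FMD and PWV fare better.

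Fourth, a label does not change how often a 95% interval excludes zero. That is true, so the fix must also bar claims drawn from intervals.

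In the other direction, 36 and 32 are minimum counts. Pairwise comparisons, paired t-tests and analyses with and without outliers would raise them. Prespecifying the sex split limits the choice of subgroup but not the error over the tests that follow.

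**Conclusion.** The point holds in conditional form. The plan runs at least 36 within-sex tests in Phase I and 32 in Phase II at two-sided 5%, without control across endpoints or sexes and without exploratory status.

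Under no true effects and exact 5% tests, the chance of at least one false positive ranges from 84% and 81% (independent endpoints) to 39% and 37% (correlation 0.8). With plausible exercise effects it is about half at correlation 0.5. Even the lowest figure shown is more than seven times 5%. Power at 10 per sex is about 0.6 for strain and higher for FMD and PWV, if r is near 0.5.

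This is a defect in what the plan allows to be concluded, and it should be corrected. It does not show that a false sex-specific claim will be made.

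**What to change.** In Protocol 9.4.7 and item 7 of SAP section 4:

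- State that the within-sex analyses are exploratory.
- Report within-sex estimates with 95% confidence intervals.
- State that no within-sex significance claim will be made, whether from a p-value or from an interval that excludes zero.
- State that no within-sex result will stand in for the full-sample result.

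Amend Protocol 9.4.9 and the matching SAP item to list these as the planned exploratory analyses.

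The cost is a few sentences in each document, with no extra participants, visits or data. The trial gives up confirmatory sex-specific claims, which 7 to 10 people per sex support poorly.

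Two related matters are left open and need their own decisions: multiplicity in the full-sample analysis (18 hypotheses at 5% in Phase I; 1 − 0.95¹⁸ = 60% if independent and all null), and the lack of a direct sex-by-condition test for the aim stated in 4.1.

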#### 9.4.8 TABULATION OF INDIVIDUAL PARTICIPANT DATA.

Data collected from each participant will be recorded by measure and study visit. Each participant will be assigned a study ID.

---

#### 9.4.9 EXPLORATORY ANALYSES

There are no planned exploratory analyses in the current study.

---

### 10 SUPPORTING DOCUMENTATION AND OPERATIONAL CONSIDERATIONS

---

#### 10.1 REGULATORY, ETHICAL, AND STUDY OVERSIGHT CONSIDERATIONS

---

##### 10.1.1 INFORMED CONSENT PROCESS

---

###### 10.1.1.1 CONSENT/ASSENT AND OTHER INFORMATIONAL DOCUMENTS PROVIDED TO PARTICIPANTS

A consent forms describing in detail the study intervention, study procedures, and risks are given to the participant and written documentation of informed consent is required prior to starting intervention/administering study intervention. The consent document is submitted with this protocol.

---

###### 10.1.1.2 CONSENT PROCEDURES AND DOCUMENTATION

Informed consent is a process that is initiated prior to the individual's agreeing to participate in the study and continues throughout the individual's study participation. The consent form has been Institutional Review Board (IRB)-approved and the participant will be asked to read and review the document. The participant will be provided the consent document in advance of their first study visit. During the first laboratory visit, an investigator will explain the study to the participant and answer any questions that may arise. A verbal explanation will be provided in terms suited to the participant's comprehension of the purposes, procedures, and potential risks of the study and of their rights as research participants. Participants will have the opportunity to carefully review the written consent form and ask questions prior to signing. The participant will sign the informed consent document prior to any procedures being done specifically for the study. Participants will be informed that participation is voluntary and that they may withdraw

from the study at any time, without prejudice. A copy of the informed consent document will be given to the participants for their records. The informed consent process will be conducted and documented in the source document (including the date), and the form signed, before the participant undergoes any study-specific procedures.

---

### 10.1.2 STUDY DISCONTINUATION AND CLOSURE

This study may be temporarily suspended or prematurely terminated if there is sufficient reasonable cause. Written notification, documenting the reason for study suspension or termination, will be provided by the suspending or terminating party to study participants, and regulatory authorities. If the study is prematurely terminated or suspended, the Principal Investigator-Sponsor will promptly inform study participants and the Institutional Review Board, and will provide the reason(s) for the termination or suspension. Study participants will be contacted, as applicable, and be informed of changes to study visit schedule.

Circumstances that may warrant termination or suspension include, but are not limited to:

- Determination of unexpected, significant, or unacceptable risk to participants
- Demonstration of efficacy that would warrant stopping
- Insufficient compliance to protocol requirements
- Data that are not sufficiently complete and/or evaluable

---

### 10.1.3 CONFIDENTIALITY AND PRIVACY

Participant confidentiality and privacy is strictly held in trust by the participating investigators. This confidentiality is extended to cover all individual test results collected during this study, in addition to the clinical information relating to participants. Therefore, the study protocol, documentation, data, and all other information generated will be held in strict confidence. No information concerning the study or the data will be released to any unauthorized third party without prior written approval of the principal investigator-sponsor.

All research activities will be conducted in as private a setting as possible.

The study monitor, other authorized representatives of the sponsor, representatives of the Institutional Review Board (IRB), regulatory agencies or pharmaceutical company supplying study product may inspect all documents and records required to be maintained by the investigator.

The study participant's contact information will be securely stored at each clinical site for internal use during the study. At the end of the study, all records will continue to be kept in a secure location for as long a period as dictated by the reviewing IRB, Institutional policies, or sponsor requirements.

Upon enrollment into the study, each participant will be assigned a participant ID. A master list of all ID's will be kept separate from all study results. Data collected will be labelled only with participant ID's. Upon completion of data collection, the master list linking identifying information to participant IDs will be destroyed. Study participant research data, which is for purposes of statistical analysis and scientific reporting, will be stored within the laboratory of [name] and will only be labelled with participant ID's. Data stored will not include the participant's contact or

identifying information. Digital study data used by research staff will be secured and password protected.

---

#### 10.1.4 FUTURE USE OF STORED SPECIMENS AND DATA

No biological specimens will be obtained in this study.

---

#### 10.1.6 CLINICAL MONITORING

Clinical site monitoring is conducted to ensure that the rights and well-being of trial participants are protected, that the reported trial data are accurate, complete, and verifiable, and that the conduct of the trial is in compliance with the currently approved protocol/amendment(s), with International Conference on Harmonization Good Clinical Practice (ICH GCP), and with applicable regulatory requirement(s).

[name] will act as the monitor for this clinical trial. She will be located on-site, and will conduct a minimum of three monitoring visits. These visits will include an initiation visit, an interim monitoring visit, and a close out visit. The initial visit will involve the PI and the investigatory team in addition to the monitor. In this meeting the protocol, investigational product, SOP's, ICH-GCP, Health Canada regulations, AE reporting, protocol deviation, and stakeholder responsibilities will be discussed to ensure all parties understand their roles in the study. During the interim visit, certain items will be reviewed for data verification for all participants, while other items will be viewed for only a selection of participants. Monitoring reports will be distributed to the entire investigatory team following the interim visit. The close out visit will involve a review of all documentation for accuracy and completeness.

---

#### 10.1.7 QUALITY ASSURANCE AND QUALITY CONTROL

Quality management of study conduct, data collection, documentation, and completion will be performed.

Following written Standard Operating Procedures (SOPs), the monitors will verify that the clinical trial is conducted and data are generated, documented (recorded), and reported in compliance with the protocol, International Conference on Harmonization Good Clinical Practice

(ICH GCP), and applicable regulatory requirements (e.g., Good Laboratory Practices (GLP), Good Manufacturing Practices (GMP)).

The investigational site will provide direct access to all trial related sites, source data/documents, and reports for the purpose of monitoring, and inspection by local and regulatory authorities. Any deficiencies or quality control issues identified by the monitor will be corrected by the investigatory team.

---

## 10.1.8 DATA HANDLING AND RECORD KEEPING

---

### 10.1.8.1 DATA COLLECTION AND MANAGEMENT RESPONSIBILITIES

Data will be recorded in encrypted digital files for the purpose of analysis. All hard copy data recorded will be archived within the lab of [name]. Regular monitoring will ensure that all hard copy data will be correct in both hard copies and electronic records. Participant's inclusion in the study will be recorded via archiving of the consent form and all hard copy data. All investigators will be held responsible for proper data handling procedures. A master list of participant IDs will be maintained throughout the course of data collection and analysis. After this period, the master list will be destroyed and all individual data will be completely de-identified.

---

